## 6.6 Additional Considerations

### 6.6.1 Precautions

An in vitro phototoxicity study in 3T3 mouse fibroblasts as well as a phototoxicity study in pigmented rats demonstrated that avapritinib has a slight potential for phototoxicity. Therefore, prolonged exposure to sunlight should be avoided during treatment. In addition, patients should take other measures to avoid ultraviolet (UV) exposure such as wearing sunscreen and sunglasses, wearing protective clothing, and avoiding tanning beds. Refer to the avapritinib IB for details.

Hypospermatogenesis was observed in the testis and epididymis of rats and dogs and did not recover after 2-week recovery. Patients should be informed of the possibility of gamete and embryo banking.

Refer to the avapritinib Investigator Brochure for details.

### 6.6.2 Contraception Requirements

Women of childbearing potential must agree to use a highly effective method of contraception (CTFG, 2014) from the time of randomization until at least 8 weeks after the last dose of study drug. Women are considered to be of childbearing potential after menarche until becoming postmenopausal (defined as no menses for at least 12 months without an alternative medical cause) unless permanently sterile. A high follicle stimulating hormone level in the postmenopausal range may be used to confirm a postmenopausal state in women not using hormonal contraception or hormonal replacement therapy. However, in the absence of 12 months of amenorrhea, a single follicle stimulating hormone measurement is insufficient. Permanent sterilization methods include hysterectomy, bilateral salpingectomy and bilateral oophorectomy (CTFG, 2014). Because avapritinib and regorafenib are potential CYP3A4 inducers, women should use hormonal contraception with caution and supplement with other highly effective methods.

Males with partners who are female of reproductive potential must agree that they will use condoms, and their partners will use a highly effective contraceptive method throughout the study, and for 90 days after the last dose of study treatment.

Highly effective forms of contraception are defined as the following (CTFG, 2014):

- Combined (estrogen and progestogen containing) hormonal contraceptives that inhibit ovulation, including oral, intravaginal and transdermal products.
- Progestogen-only hormonal contraceptives that inhibit ovulation, including oral, injectable, and implantable products.
- Intrauterine devices (IUD) and intrauterine hormone-releasing system (IUS).

- Bilateral tubal occlusion (women).
- Male partner vasectomy or other method of surgical sterilization provided that the partner is the sole sexual partner of the trial participant and the vasectomized partner has received medical assessment of the surgical success.
- Sexual abstinence (men and women), when this is the preferred and usual lifestyle of the patient. Periodic abstinence (such as calendar, symptothermal and postovulation methods), withdrawal (coitus interruptus), and the lactational amenorrhea method are not acceptable methods of contraception.

The following methods of contraception are not considered highly effective ([CTFG, 2014](#)):

- Progesterone-only oral hormonal contraception that do not inhibit ovulation.
- Barrier methods with or without spermicide, or spermicide alone.

## 7 DESCRIPTION OF STUDY PROCEDURES

### 7.1 Screening

After informed consent, all patients will undergo screening procedures within 28 days before dosing on C1D1 to determine eligibility. Patients may be randomized in the system at any time but must be dosed within 28 days of signing of informed consent.

The following procedures will be performed at the Screening visit:

- Obtain demographic data, including sex, date of birth/age, race, and ethnicity;
- Complete medical history, including a history of GIST and/or other malignancies, prior treatments, the response to each treatment if available, and concurrent illnesses;
- Complete physical examination and a basic neurological assessment, including ECOG PS;
- Vital signs including weight, temperature, pulse, and systolic/diastolic blood pressure. Height will also be measured at Screening;
- 12-lead ECG;
- Obtain plasma sample for exploratory biomarkers and ctDNA mutation testing;
- Clinical laboratory assessment (hematology, coagulation, serum chemistry, and urinalysis);
- Serum pregnancy test (women of childbearing potential only);

- Tumor imaging by CT with IV contrast or MRI (CT is required for the chest and preferred for all body regions unless a site of disease is better imaged by MRI). If a patient is intolerant of IV contrast, CTs may be performed without IV contrast.
- Brain imaging by MRI or CT (MRI is preferred, if available);
- Recording of concomitant medications and SAEs. Concomitant medications and SAEs are to be collected from the date of the informed consent signature through the Safety Follow-up Assessment, while AEs are to be collected from start of study drug administration through the Safety Follow-up Assessment.

## 7.2 Safety Assessments

The schedule of safety assessments is described in [Table 2](#). All clinical and laboratory safety assessments will be assessed by the Investigator for clinical significance and clinically significant findings will be reported as AEs. Additional safety assessments may be performed if dictated by the local standard of care and when clinically indicated, at the Investigator's discretion.

### 7.2.1 Physical Examination

A complete physical examination including a basic neurological assessment will be performed at the Screening visit. Subsequent physical examinations will be performed as outlined in [Table 2](#), and will focus on symptoms and signs of GIST, changes from previous physical examinations, and AEs.

### 7.2.2 Eastern Cooperative Oncology Group Performance Status

Determination of ECOG PS will be performed at the time points outlined in [Table 2](#). Refer to [Appendix 5](#) for ECOG PS scoring.

### 7.2.3 Brain Imaging

Brain imaging by MRI or CT (MRI is preferred) will be performed at the visits outlined in [Table 2](#), and should be repeated as clinically indicated, ie, for unexpected neurologic AEs. Patients who have been on study for more than 12 weeks should have imaging performed at the next scheduled visit and 12 weeks later ( $\pm 1$  week).

### 7.2.4 Vital Signs

Vital sign measurements will include temperature, systolic/diastolic blood pressure, pulse, and weight, and will be performed at the time points outlined in [Table 2](#). Height will be measured at the Screening visit only.

Blood pressure and pulse assessments should be conducted while the patient is seated or supine.

**7.2.5 ECGs**

Twelve-lead ECGs will be obtained for all patients at the time points outlined in [Table 2](#).

Twelve-lead ECGs are to be conducted after 5 minutes in recumbence or semi-recumbency.

**7.2.6 Clinical Laboratory Tests**

Clinical laboratory evaluations for safety will be performed at a central laboratory. Before starting the study, the Investigator will provide the Sponsor (or its designee) copies of all laboratory certifications and normal ranges for all laboratory assessments to be performed by that laboratory. Local laboratory assessments may be used to make treatment-related decisions.

Clinical laboratory evaluations will be conducted at the time points outlined in [Table 2](#). In addition, all clinically significant laboratory abnormalities noted on testing will be followed by repeat testing and further investigated according to the judgment of the Investigator.

The following safety laboratory tests are to be evaluated by the Investigator:

Hematology:	Hemoglobin, red blood cell count (RBC), white blood cell count (WBC) with differential (including ANC), and platelet count
Coagulation:	Prothrombin time (PT), international normalized ratio (INR), and activated partial thromboplastin time (aPTT)
Serum chemistry:	Sodium, potassium, blood urea nitrogen (BUN) or urea, bicarbonate (venous), creatinine, calcium, chloride, magnesium, phosphorus, albumin, AST, ALT, alkaline phosphatase (ALP), total bilirubin (direct bilirubin if total > ULN)
Urinalysis (dipstick):	pH, specific gravity, bilirubin, blood, glucose, ketones, leukocyte esterase, nitrite, protein, and urobilinogen
Serum or urine pregnancya:	$\beta$ -hCG

a A serum pregnancy test should be performed for women of childbearing potential at Screening and at C1D1. A serum or urine pregnancy test should be performed every 4 weeks through 8 weeks after the last dose of study drug.

**7.2.7 Adverse Events and Concomitant Medications**

Each patient must be carefully monitored for the development of any AEs throughout the study from C1D1 (or from the time of signing informed consent, for SAEs) to 30 days

after the last dose. In addition, SAEs that are assessed as related to study treatment that occur > 30 days after the last dose also are to be reported.

Complete details on AE and SAE monitoring are provided in [Section 9](#).

Concomitant medications will be recorded from the time of signing informed consent to 30 days after the last dose.

### **7.3 Pharmacokinetic Assessment**

Blood samples will be collected from patients in Arm A of the study (those receiving avapritinib) before and after study drug dosing to determine circulating plasma concentrations of avapritinib (including any relevant metabolites). There will be no PK samples collected from patients in Arm B of the study (those receiving regorafenib).

Pharmacokinetic samples will be collected before dosing (ie, predose) on Day 1 of Cycles 1, 2, 3, and 5. On C2D1, additional samples will be collected predose and at 1 hour ( $\pm 10$  minutes), 4 hours ( $\pm 15$  minutes), and 6-8 hours ( $\pm 15$  minutes) postdose in a total of 25 patients at selected centers. On C3D1 and C5D1, in addition to the predose sample, samples will be collected at any 1 time point between 1-8 hours postdose. Note: The predose sample is to be collected before the day's dose of avapritinib and should be taken as close as possible to 24 hours after the prior dose was taken.

Additionally, Investigators may obtain blood samples for PK analysis at the time(s) that significant drug-related AEs and SAEs occur.

### **7.4 Blood Samples for Biomarker Assessment**

Blood samples will be collected for patients at the time points outlined in [Table 2](#) to characterize the mutant allele fraction in plasma ctDNA at Baseline, each visit thereafter, and at end of treatment to measure changes from Baseline in the levels of KIT, PDGFR $\alpha$ , and other cancer-relevant mutant allele fractions.

### **7.5 Efficacy Assessments**

#### **7.5.1 Disease Response Assessment**

Blinded central radiology review of disease response or disease progression (per Choi criteria and per mRECIST, version 1.1) will be based on local imaging scans performed at the time points outlined in [Table 2](#). Note that tumor imaging should occur every 8 weeks ( $\pm 1$  week) from Cycle 1 Day 1 regardless of the scheduled treatment cycles ie, if study treatment is interrupted or discontinued for any reason, tumor imaging should continue according to an 8-week schedule until disease progression or death.

Computed tomography with IV contrast of the chest, CT or MRI with IV contrast of the abdomen and pelvis will be performed at Screening. At subsequent timepoints, the abdomen, pelvis, and all other body regions that contained sites of disease (target or non-target) at Screening will be imaged. Computed tomography of the chest is not required if

there were no sites of disease in the chest at Screening. Computed tomography with IV contrast is the preferred imaging modality, unless a site of disease is better evaluated by MRI. If a patient is not tolerant of IV contrast, non-contrast scans may be performed. For each patient, the same method of tumor imaging used at Baseline should be used throughout the study.

Computed tomography and MRI scans will be reviewed locally at the study center, ideally by the same individual for each patient at each time point, and disease response and progression will be assessed per mRECIST, version 1.1. Computed tomography and MRI scans will also be collected and reviewed centrally to provide a central assessment of response and progression, both per mRECIST, version 1.1 and per Choi criteria.

Patients on either treatment arm considered by local assessment to have disease progression shall not discontinue treatment until progression (per mRECIST, version 1.1) has been confirmed by central radiology review. Patients may only cross over from regorafenib treatment to avapritinib treatment if disease progression has been confirmed by central radiology review.

### **7.5.2 Central Radiology Review**

A blinded central radiology review will be performed according to a prospectively established central imaging charter and conducted by an external imaging contract research organization. The central radiology review will be chartered to evaluate response assessment independently per mRECIST, version 1.1. ([Appendix 6](#)) and per Choi criteria ([Appendix 7](#)).

A detailed study-specific Imaging Core Manual will be made available to sites regarding scan acquisition requirements. All radiological scans acquired at all scheduled time points and any additional (unscheduled) radiological scans must be sent to the external imaging contract research organization.

### **7.5.3 Quality-of-Life Instruments**

Patients will complete the EORTC-QLQ-C30 at scheduled clinical site visits up to the EOT visit, as outlined in Table 2. These assessments are provided in Appendix 8 (EORTC-QLQ-C30).

### **7.5.4**

## 7.6 Crossover From Regorafenib to Avapritinib

Patients who experience disease progression while receiving regorafenib (Arm B), as confirmed by central radiology review, may be offered the opportunity to cross over to the avapritinib treatment arm (Arm A).

Patients who cross over to avapritinib must complete a washout period of 7 to 28 days after their last dose of regorafenib and consent to cross over before starting treatment with avapritinib. At the first study visit after the washout period, cross over patients will complete the C1D1 assessment schedule except for the following tests, which are not required: PK blood sample and biomarker plasma sample. Otherwise patients who crossed over will follow the same schedule of assessments as on the main portion of the Protocol (except C1D15 or C2D15 visits, which are not required). After patients cross over to treatment with avapritinib, ECGs will be performed following the same schedule as prior to cross over and AEs will only be assessed for their relationship to avapritinib.

## 7.7 Continuing Avapritinib After Disease Progression

Patients who experience disease progression while receiving avapritinib (Arm A), as confirmed by central radiology review, may be offered the opportunity to continue treatment with avapritinib if the following criteria are met:

- There are no symptoms or signs indicating clinical disease progression (including worsening of laboratory values).
- The patient is not experiencing rapid progression of disease or a progressive tumor requiring urgent alternative medical intervention at critical anatomical sites (eg, spinal cord compression).
- There has been no decline in ECOG PS

Patients randomized to Arm A must consent to continue avapritinib treatment after disease progression. This consent must be obtained after disease progression has occurred.

## 7.8 End-of-Treatment, Safety Follow-up and Progression-Free Survival Follow-up

All patients will attend an EOT visit approximately 14 days ( $\pm$  7 days) after the last dose of study drug (see [Table 2](#) for a description of EOT assessments). If an alternative antineoplastic treatment is started within 14 days of the last dose of study drug, the EOT visit should be conducted before the first dose of the alternative antineoplastic therapy. Tumor assessment for EOT procedures do not need to be repeated if they were performed within 7 days (or within 28 days for disease response assessments).

A Safety Follow-up visit (clinic visit or a phone call) for resolution of any ongoing AE will be made 30 days ( $\pm$  7 days) after the last dose of study drug, or at the time the patient initiates another antineoplastic therapy.

Thereafter, patients without documented PD will be followed approximately every 8 weeks ( $\pm 7$  days) until disease progression, death, initiation of new anti-GIST therapy, withdrawal of consent, or closure of the study by the Sponsor.

## **7.9 Survival Follow-up**

After documentation of disease progression by central radiology review, patients or their designated care giver will be contacted by phone every 2 months until withdrawal of consent, death, or closure of the study by the Sponsor to collect the drug name of any new systemic antineoplastic therapy or the date of death.

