At least 70% of the patients enrolled should be receiving the study drug as their third distinct TKI treatment for GIST, ie, no more than 30% of patients should be receiving the study drug as their fourth distinct TKI treatment for GIST. In addition, patients will

receive BSC, excluding any additional anticancer therapy such as any systemic antineoplastic therapy (including kinase inhibitors and chemotherapy), radiation therapy, or surgery.

All patients will present to the study center on C1D1 for the first dose of study drug, vital sign measurements, physical exam, quality-of-life (QoL) assessment, PRO assessments, laboratory assessments, ECG and AE recording. In Cycle 2 Day 1 (C2D1), Cycle 3 Day 1 (C3D1), Cycle 4 Day 1 (C4D1) and Cycle 5 Day 1 (C5D1), patients will present to study centers for physical examination, vital signs measurements, laboratory assessments, QoL assessments, PRO assessments, ECG, and AE/concomitant medication recording. On C1D15 and C2D15, all patients will attend study center visits for vital sign measurements, serum chemistry measurements, and AE reporting. For all subsequent cycles, all patients will attend study center visits every other cycle on Day 1 of odd cycles (ie, C7D1, C9D1 etc.) for physical examination, vital sign measurements, laboratory assessments, QoL assessments, PRO assessments, ECG and AE recording. At any point in time between treatment cycles patients should attend or contact the study center for AE reporting, evaluation, and medical intervention.

[figure not shown]
Tumor assessments will be performed at Baseline and then every 8 weeks ( $\pm$  1 week) counting from C1D1, regardless of the scheduled treatment cycles, ie, if study treatment is interrupted or discontinued for any reason, tumor imaging should continue according to an 8-week schedule until tumor progression is confirmed by central radiology review. Computed tomography with intravenous (IV) contrast is the preferred imaging modality, unless a site of disease is better evaluated by MRI.

It is anticipated that patients will receive at least 1 cycle of avapritinib if randomized to Arm A and regorafenib if randomized to Arm B; no maximum treatment duration has been set. After C1, patients may continue to receive study drug until precluded by toxicity, noncompliance, pregnancy, withdrawal of consent, physician decision, PD, death, or closure of the study by the Sponsor.

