All patients will attend an End-of-Treatment (EOT) visit within 14 ( $\pm$ 7) days after the last dose of study drug. A safety Follow-up visit for resolution of any ongoing AE will be made on Day 30 ( $\pm$ 7 days) after the last dose of study drug, or at the time the patient initiates another antineoplastic therapy. Patients who discontinue study treatment before disease progression will undergo tumor assessments every 8 weeks until disease progression, death, or patient withdrawal of consent. After documentation of disease progression by central radiology review, patients are to be followed for subsequent antineoplastic therapy and survival approximately every 2 months until death, withdrawal of consent or closure of the study by the Sponsor.

The expected enrollment period is approximately 18 months, and the expected duration of the study to reach the primary analysis timepoint is approximately 24 months until a total number of 264 PFS events are reached. The study will be completed when all patients are no longer receiving study drug and follow-up for OS has been concluded.

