## 6 STUDY CONDUCT

### 6.1 General Conduct

The study will be conducted at multiple centers in North America, Europe, Australia, and Asia.

This study will be conducted in compliance with the protocol, Good Clinical Practice (GCP), and the applicable regulatory requirements.

Patients may be randomized in the system at any time but must be dosed within 28 days of signing of informed consent.

The schedule of assessments for the study is provided in [Table 2](#).

The minimum duration of patient participation is expected to be approximately 3 months, including a screening period to assess study eligibility up to 4 weeks (28 days); a treatment period of at least 1 cycle (28 days); an EOT visit at least  $14 \pm 7$  days after the last dose of study drug; and a Safety Follow-up visit in the clinic for physical examination and resolution of any AEs 30 days ( $\pm 7$  days) after the last dose of study drug. Thereafter, patients are to be followed for tumor imaging every 8 weeks ( $\pm 7$  days) until disease progression, death, initiation of new anti-GIST therapy, withdrawal of consent, or closure of the study by the Sponsor and then survival approximately every 2 months until death, withdrawal of consent or closure of the study by the Sponsor.

The end of the study is defined as the time that the last patient completes his/her last visit (LPLV), including assessments performed as part of PFS follow-up, if the patient enters the PFS follow-up part of the study. See [Section 7](#) for details of all study assessments.

The expected enrollment period is approximately 18 months and the expected duration of the study to reach the primary analysis timepoint is approximately 24 months until a total number of 264 PFS events are reached. The study will be completed when all patients are no longer receiving study drug and follow-up for OS has been concluded.

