##### **4.2 Patient Disposition**

The number and percent of patients will be tabulated for the ITT, Safety, PP, and RE Populations, respectively, for the following categories:

- Patients in the population
- Patients who receive study treatment
- Patients who end main study treatment without continuation or cross-over to avapritinib
- Patients who continue or cross-over to avapritinib
- Patients who end treatment after continuation or cross-over to avapritinib
- Patients who receive subsequent anti-cancer therapy

Reasons for treatment discontinuation will be summarized with the following categories collected on the electronic case report form (eCRF):

- Patient refuses treatment
- Withdrawal of consent
- Pregnancy
- Adverse event and related adverse event
- Disease progression (confirmed by Central Review)
- Clinical progression
- Protocol deviation

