#### *4.6.3.2 Overall Survival*

Overall survival is defined as the time from randomization to the date of death. Patients who die before or on the data cutoff date will be considered to have had an OS event. All patients who do not have a death record prior to or on the cutoff date will be censored at the last date known alive.

The primary treatment comparison will be based on a stratified log-rank test using the ITT Population. The HR and its 95% CI will be estimated using a stratified Cox model with treatment as the explanatory variable and strata as the stratification factors. An unstratified log-rank test will be performed as a sensitivity analysis.

A rank preserving structural failure time (RPSFT) model will be applied as a supportive analysis to account for treatment crossover effects from regorafenib to avapritinib. The survival time gained/lost by receiving avapritinib after crossover in the regorafenib group will be estimated. The RPSFT reconstructs the survival duration of crossover patients as if they had never received avapritinib, assuming treatment acts by multiplying survival time by a given factor once a patient starts receiving avapritinib (Korhonen et al, 2012). See Appendix 2 (Section 7.4) for further details of implementing this method.

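### Survival follow-up has conflicting start rules: under Protocol 7.8, 7.9 and Table 2, a patient who starts new anti-GIST therapy before centrally documented progression has no survival contact, whereas 6.1 continues it

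*Protocol*

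**What the plan says.** The Protocol describes the hand-over from tumor imaging to survival contact in three ways.

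- **Sections 7.8 and 7.9, with Table 2 notes g and h.** Patients without documented progression are followed "until disease progression, death, initiation of new anti-GIST therapy, withdrawal of consent, or closure of the study by the Sponsor". Survival calls then have a single trigger: "After documentation of disease progression by central radiology review, patients or their designated care giver will be contacted by phone every 2 months".
- **Section 6.1 and the synopsis entry on duration of patient participation.** Imaging stops at the same list of events, but the sentence goes on: "initiation of new anti-GIST therapy, withdrawal of consent, or closure of the study by the Sponsor and then survival approximately every 2 months until death". Survival contact follows the end of imaging, including an end caused by new therapy.
- **Section 4.1 and the synopsis study design text.** New therapy does not end imaging: "Patients who discontinue study treatment before disease progression will undergo tumor assessments every 8 weeks until disease progression, death, or patient withdrawal of consent". Survival contact follows centrally documented progression.

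For the analysis, SAP Section 4.6.3.2 states: "All patients who do not have a death record prior to or on the cutoff date will be censored at the last date known alive". SAP Section 3.2.6 defines that date as the last non-imputed date of any patient record up to the cutoff.

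**The concern.** New anti-GIST therapy is an exit from imaging in 7.8 but not an entry to survival follow-up in 7.9. A patient who stops study drug, for example for an adverse event or by investigator decision (both allowed in Section 5.7), and starts another agent before central progression meets the exit and never meets the entry condition. The plan expects such patients: Protocol Section 10.5.3.1 and SAP Table 2 both contain a PFS censoring rule for new therapy before progression.

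OS is a key secondary endpoint, third in the error-controlled sequence after PFS and objective response rate, and it is analysed in all randomized patients. If scheduled contact stops around the switch, the OS censoring date falls near the switch too. Patients who change therapy early may differ in prognosis from those who stay, so this censoring could be informative.

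The trial is open-label, and only Arm B patients need central confirmation of progression to cross over to avapritinib (Sections 7.5.1 and 7.6). The chance of a switch without central progression could therefore differ by arm. The documents do not establish whether it does, or in which direction.

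**Working it through.** **Step 1. The rules side by side**, for a patient who starts new therapy before central progression:

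| Source | Imaging ends at | Survival contact starts at | Result for this patient |
|---|---|---|---|
| 7.8, 7.9; Table 2 notes g, h | progression, death, new therapy, consent withdrawal, study closure | centrally documented progression | leaves imaging; survival contact never triggered |
| 6.1; synopsis participation text | same list | end of imaging | moves to survival contact |
| 4.1; synopsis design text | progression, death, consent withdrawal | centrally documented progression | stays in imaging; survival contact after central progression |

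The three rows cannot all be followed. Section 7.5.1 and Table 2 note t agree with the third row in continuing imaging after treatment stops without naming new therapy as an end, so Protocol Table 2 also disagrees with itself (note g against note t).

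**Step 2. Where the censoring date falls.** Under the first row, scheduled contact after the switch is at most what remains of the end-of-treatment and 30-day safety visits. With SAP 3.2.6 and 4.6.3.2, a patient with no later record is censored for OS at about that time.

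**Step 3. Reproduce the planned number of deaths.** Inputs from Protocol Section 10.2: hazard ratio 0.67, two-sided alpha 0.05, power 90%, 1:1 allocation, the same effect assumed for OS as for PFS.

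- Schoenfeld: d = 4(z₀.₉₇₅ + z₀.₉₀)² / (ln HR)² = 4(1.960 + 1.282)² / (0.4005)² ≈ 42.03 / 0.1604 ≈ 262.0, rounded up to 263. Freedman's formula gives 270.
- Power at 264 deaths: Φ(½ × √264 × 0.4005 − 1.960) = 0.902.

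The stated 264 is reproduced. It is 264/460 = 57.4% of the planned sample.

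**Step 4. What incomplete capture would do.** The documents give no rate, so the share f is an assumption. Two separate questions follow. If a share f of patients has no death capture, the fraction of the remainder who must die to reach 264 is 264 / [460(1 − f)]. If instead the analysis were run with a share f of the 264 deaths unobserved, power is the Step 3 expression at 264(1 − f) deaths.

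| Assumed f | Patients (f × 460) | Remainder who must die | Power at 264(1 − f) deaths |
|---|---|---|---|
| 0 | 0 | 57.4% | 90.2% |
| 5% | 23 | 264/437 = 60.4% | 88.7% (250.8 deaths) |
| 10% | 46 | 264/414 = 63.8% | 87.0% (237.6 deaths) |
| 15% | 69 | 264/391 = 67.5% | 85.1% (224.4 deaths) |

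The final OS analysis is event-driven, so the third column is the relevant one and shows delay. The last column would apply only if the analysis did not wait for 264 recorded deaths. Neither column measures bias from informative censoring.

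**The case against.** **Survival follow-up after new therapy is written down elsewhere.** Section 6.1 and the synopsis state it outright, and no section is ranked above another. SAP Section 4.2 does not name new therapy among the reasons for leaving the study, so the plan can be read as keeping these patients on study. This stands: the defect is an inconsistency, and loss of vital status is possible, not certain. It does not remove the conflict, because Section 7 and the schedule of assessments give the narrower trigger.

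**A reader might infer that patients who stop for clinical progression are also lost.** Section 7.8 says progression without a central qualifier while 7.9 requires central review, and SAP Section 4.2 lists "Clinical progression" apart from centrally confirmed progression. The documents do not support going that far. The SAP item is a reason for stopping treatment, not follow-up. Under Section 4.1, after treatment stops for any reason, "tumor imaging should continue according to an 8-week schedule until tumor progression is confirmed by central radiology review". Section 7.5.1 also bars stopping treatment on locally assessed progression before central confirmation. Such a patient clearly enters the gap only on starting new therapy.

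**A reader might count Section 4.1 as part of the gap.** Read alone it has none, because imaging continues past new therapy until progression. Its fault is disagreement with 7.8.

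**A reader might turn the 23 to 69 patients into lost deaths:** 23 × 0.574 ≈ 13 and 69 × 0.574 ≈ 40, or 5% to 15% of 264. That is a worst case on an assumed range. It supposes that every site disregards 6.1 and the synopsis, that no death is learned of by another route, and that the overall death fraction applies to this subgroup. It also treats as lost information what would mainly be delay.

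**Conclusion.** The concern holds as a conflict between operative rules. Under 7.8, 7.9 and Table 2 notes g and h, a patient who switches therapy before central progression has no survival contact. Under 6.1 and the synopsis participation text the patient does, and 4.1 with the synopsis design text gives a third rule. The consequence is potentially informative censoring of OS near the switch at sites that follow the narrower wording.

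The size cannot be derived from the documents. It depends on how many patients switch before central progression and which section each site follows. For the final analysis, missed deaths would chiefly postpone reaching 264. The interim OS analysis planned with the final PFS analysis would use whatever deaths had been recorded by then. Any bias from informative censoring would not be cured by waiting, and its size and direction are unknown.

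**What to change.** Use one survival trigger throughout. Align 7.9, Table 2 note h, 4.1 and the synopsis design text with 6.1, so that survival contact starts for every randomized patient when imaging follow-up ends for any reason other than death, withdrawal of consent for survival contact, or closure of the study.

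Separately, reconcile 4.1 (with 7.5.1 and Table 2 note t) and 7.8 (with note g) on whether imaging stops at new therapy. The choice also affects the sensitivity analysis of PFS under the EMA rules in SAP Table 2, which counts progression or death after new therapy as an event and so needs those data.

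The cost is a short wording change and a few more phone calls. It should be made while follow-up is running, because vital status not collected prospectively may be hard to recover.
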